#### Virologic variables at regimen initiation

- HIV VL at initiation of CAB+RPV LA regimen
  - o Categorical:
    - <50 copies/mL

    - Individuals with ≥50 copies/mL at regimen initiation should not be included in the study. copies/mL

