#### 8.7. Data analysis

All enrolled participants who receive at least one dose of the CAB+RPV LA regimen will be included in the analysis. Participants who are prescribed but never receive a dose of CAB+RPV LA regimen will be excluded from the analysis. Study results will be stratified by the regimen used (Q4/Monthly dosing vs Q8/Every 2 month dosing). Further, study results for co-infected patients with hepatitis B or C will be presented separately. All continuous variables will be summarized using the following descriptive statistics: n (non-missing sample size), mean, standard deviation, 1st quartile, median, 3rd quartile, maximum and minimum. The frequency and percentages (based on the non-missing sample size) of observed levels will be reported for all categorical variables. Data will be analyzed using SAS®, SPSS® or STATA®.

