# Assessment of factors associated with non-adherence, virologic failure, discontinuation and resistance

Univariable and multivariable analyses will be performed to identify factors that probably modified the effect of the study treatment on the risk of outcomes of interest. Cox regression models will be used to assess the factors associated with virologic failure, with non-adherence and with the discontinuation of CAB+RPV LA regimen. Logistic regression will be used to assess factors associated with drug resistance among participants with virological failure, if the number of events allow this analysis. Variables with univariable P<0.20 will be retained for the multivariable analysis.

All variables described at section 8.3.3 will be assessed. We will assess whether continuous variables will be better modelled as continuous variables or as terciles based on the lowest value of Akaike's information criterion (AIC) for the corresponding univariable Cox regression models or univariable logistic regression models according to the outcome of interest, and grouped together the closest values in order to obtain two classes for certain variables.

Sensitivity Analysis: As some parameters with missing data can influence the outcome of interest, to quantify the potential effect, we will create 5 datasets in which missing data will be replaced using Rubin's multiple imputation method. Instead of filling in a single value for each missing value, multiple imputation procedure replaces each missing value with a set of plausible values that represent the uncertainty about the right value to impute. Analyses will be run on each of the 5 data sets, and the results will be combined with Rubin's rules. Pooling the multiple parameter estimates from the 5 datasets into one estimate along with its variance (which combines the conventional sampling variance and the extra variance caused by the missing data) will help understand the effect of the missing data.

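### Fixing the multiple-imputation sensitivity analysis at 5 datasets leaves its pooled P values and interval limits dependent on the random seed; at least 50 would cost only computing time

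*Protocol*

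**What the plan says.** The relevant text is in Protocol section 8.7, under the heading on factors associated with non-adherence, virologic failure, discontinuation and resistance.

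- **Models.** Cox models are planned for virologic failure, non-adherence and discontinuation, and a logistic model for resistance. On candidate variables the text says "All variables described at section 8.3.3 will be assessed", and on selection "Variables with univariable P<0.20 will be retained for the multivariable analysis".
- **Imputation.** The paragraph opens "Sensitivity Analysis: As some parameters with missing data can influence the outcome of interest" and continues "we will create 5 datasets in which missing data will be replaced", by Rubin's method. On pooling: "Analyses will be run on each of the 5 data sets, and the results will be combined with Rubin's rules". The number 5 appears three times in the paragraph, so it is a definite choice and not a detail left open.
- **Purpose.** The stated aim is to quantify what the missing data may do to the results.
- **Not stated.** The protocol gives no missing-data rate for any variable, and it does not say how the main regression models treat a missing covariate.

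**The concern.** Multiple imputation draws at random. With few draws, the pooled estimate, its standard error and its P value change when the same procedure is rerun on the same data with another seed. Five draws is a small number for results that will be read as P values and confidence limits.

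The analysis exists to compare imputed with main results. If the two differ by less than the noise between seeds, the difference says nothing about missing data, and the reader of the report cannot tell. If the univariable screen at P<0.20 were also rerun on imputed data, which the protocol does not specify, the seed could affect which variables enter the model.

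Some missingness is to be expected. The data come from routine records, and the case report form in Annex 1 asks whether height and weight are available and takes the subtype group only where it is known.

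**Working it through.** **Inputs.** The number of imputations, m = 5, and pooling by Rubin's rules come from section 8.7. The FMI is not in the document, so it is assumed, over 0.05 to 0.5. The protocol has no figure of its own on the adequacy of m = 5, so there is none to reproduce.

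**1. Efficiency of the point estimate.** Relative efficiency = 1/(1 + FMI/m). With m = 5:
- FMI 0.1: 1/(1 + 0.02) = 0.98
- FMI 0.3: 1/(1 + 0.06) = 0.94
- FMI 0.5: 1/(1 + 0.10) = 0.91

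On this criterion five imputations are adequate.

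**2. Noise between seeds.** Take the total variance as 1. The between-imputation variance is B = FMI/(1 + 1/m), and the Monte Carlo standard error (MCSE) of the pooled estimate, in units of its own standard error, is √(B/m). At FMI 0.3 and m = 5: B = 0.3/1.2 = 0.25, and MCSE = √(0.25/5) = 0.224.

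**3. Effect on a P value of 0.05.** Take z = 1.96 ± 1.96 × MCSE and convert both ends to two-sided P values. At FMI 0.3 and m = 5: z = 1.96 ± 0.438, so 1.522 to 2.398, and P = 0.128 to 0.016. The same steps give:

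| FMI (assumed) | MCSE, m = 5 | P range, m = 5 | MCSE, m = 50 | P range, m = 50 |
|---|---|---|---|---|
| 0.05 | 0.091 | 0.032-0.075 | 0.031 | 0.043-0.058 |
| 0.1 | 0.129 | 0.027-0.088 | 0.044 | 0.041-0.061 |
| 0.3 | 0.224 | 0.016-0.13 | 0.077 | 0.035-0.070 |
| 0.5 | 0.289 | 0.012-0.16 | 0.099 | 0.031-0.077 |

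**4. Cross-check by simulation.** The formula treats the pooled standard error as known. A simulation of 200,000 draws also let the between-imputation variance vary and used Rubin's degrees of freedom. For a true P of 0.05 and m = 5, the central 95% ranges were 0.024-0.107 (FMI 0.1), 0.011-0.201 (0.3) and 0.004-0.287 (0.5). With m = 50 and FMI 0.3 the range was 0.032-0.078. The formula therefore understates the instability at m = 5.

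**5. Effect on the comparison of main and imputed results.** With m = 5 the seed alone can move an estimate, and its confidence limits with it, by 1.96 × MCSE: 0.18 standard errors at FMI 0.05, 0.44 at FMI 0.3 and 0.57 at FMI 0.5. With m = 50 and FMI 0.3 the figure is 1.96 × 0.077 = 0.15.

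**The case against.** **Missing information may be small.** A coefficient's FMI is usually near the missing rate of its own covariate. If each variable were 2% to 5% missing, FMI would be roughly 0.02 to 0.05. At m = 5, a P value of 0.05 would then range over only 0.038-0.065 or 0.032-0.075. The second range is close to what 50 imputations give at FMI 0.3. This stands: the wide ranges need heavier missingness, and the document neither shows it nor rules it out.

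**No decision hangs on the P value.** Section 8.4 says that no formal hypothesis is tested, and section 8.7 sets no significance level for the multivariable models. The purpose is to compare estimates, and those are 91% to 98% efficient. This lowers the stakes. It does not remove the noise from the comparison or from the reported intervals.

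**A stronger reading goes too far.** A reader might infer that, because imputation is only a sensitivity analysis, the main model drops every incomplete record across some 25 covariates and so loses most of its few failures. The documents do not support this, for four reasons:
- The variables in section 8.3.3, 24 items by count, are candidates. Only those passing P<0.20 go forward, about 24 × 0.20 ≈ 5 if none were associated. Baseline viral load has a single level by design: "Individuals with ≥50 copies/mL at regimen initiation should not be included in the study".
- A complete-case main model is nowhere written. The nearest text is "The frequency and percentages (based on the non-missing sample size) of observed levels will be reported for all categorical variables", which concerns descriptive tables. How the regressions treat missing covariates may be set in the statistical analysis plan, which is not at hand.
- Multiplying missingness across variables assumes independence. In Annex 1 the comorbidities share one opening question, and height and weight share one availability question, so gaps would tend to cluster.
- Few failures, 20 to 60 in section 8.4, is a feature of the virologic failure and resistance models. At 8% to 16% of 1000, discontinuation would give 80 to 160 events.

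Nor does it follow that the imputed model should be the main one. That would make the main result depend on an imputation model and on a missing-at-random assumption, which is a trade-off and not a correction.

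**Conclusion.** The point holds in a limited form. The protocol commits to 5 imputed datasets. That is enough for efficient point estimates but not for reproducible P values and interval limits unless missing information is small. By the formula, a P value of 0.05 spreads over 0.032-0.075 at FMI 0.05 and 0.012-0.16 at FMI 0.5. The conclusion rests on the assumed FMI values and on the usual normal approximation; allowing for Rubin's degrees of freedom makes the ranges wider. The reach is one exploratory sensitivity analysis, and the descriptive estimates for the four aims do not use it. This is a minor improvement that is nearly free, not a defect that threatens the study's conclusions.

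**What to change.** In the sensitivity analysis paragraph of section 8.7, replace 5 datasets by at least 50, or by at least the percentage of incomplete cases if that is higher, and change the other two mentions of 5 to match. At FMI 0.3 the range for a P value of 0.05 narrows from about 0.016-0.13 to about 0.035-0.070. The cost is computing time and a wording change. Data collection, sites, participants and the role of imputation as a sensitivity analysis all stay as they are.

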### 8.8. Quality control and Quality Assurance

Site selection and training of site staff will ensure suitably qualified personnel are involved at every stage of the data gathering process. Data will be analyzed using SAS, SPSS or STATA.

#### 8.9. Limitations of the research methods

Limitations of this study are common to non-randomized non-interventional study. This is a study of routine clinical care and reflects treatment practice across NEAT ID Network clinical sites. Confounding by indication, whereby persons are selected for specific regimens, cannot be ruled out. While the study aims to include approximately 1000 PLWH on CAB+RPV LA regimen, market uptake of the regimen, individuals' willingness to participate will dictate how quickly data will be collected. Following up of study participants for 4 years after discontinuation of the CAB + RPV LA regimen will increase the potential for loss to follow up as would be expected, in a real world setting. The results from this study should be interpreted cautiously, with careful consideration given to the limitations of the observational study design.

#### 9. PROTECTION OF HUMAN SUBJECTS

#### 9.1. Ethical approval and subject consent

Before the start of data collection, this protocol and any accompanying material to be provided to the participants (subject information sheets, or descriptions of the study used to obtain informed consent) will be submitted to Ethics Committee (EC) in the relevant countries. The participating clinical sites will not begin any study activities until approval from the EC has been documented and the Sponsor (MAH) has provided as an activation letter to the clinical site investigator.

Any subsequent amendments that require review by EC will not be implemented until the EC grants the amendments a favourable opinion which will be disseminated to the investigator and sites (NOTE: amendments may also need to be reviewed and accepted by the regulatory agencies and/or local EC departments before they can be implemented in practice at sites) In accordance with the requirements of the EC, an annual progress report will be submitted as needed to the EC. NEAT ID team will notify the EC of the end of the study. If the study is ended prematurely, NEAT ID will notify the EC, including the reasons for the premature termination.

### 9.2. Subject confidentiality

All investigators and study site staff will comply with the requirements of the current Data Protection Regulations with regards to the collection, storage, processing and disclosure of personal information and will uphold the Regulation's core principles.

Only deidentified data is reported to the central study database. Identifiable
individual information (held only by the site investigator in routine medical
records) will be kept secure at all times and maintained in line with local
applicable standard operating procedures. Access to this will be to the minimum
number of individuals necessary for quality control, and audit reasons. There will
be no entry of any identifiable data into the study database at any time.

# 10. MANAGEMENT AND REPORTING OF ADVERSE EVENTS/ADVERSE REACTIONS

There is no potential to collect individual level data on serious and non-serious adverse events (AEs), pregnancy exposures, device deficiencies and device related events or incidents related to any ViiV Healthcare product during the conduct of this research, as the minimum criteria needed to report AEs, pregnancy exposures, and incidents are not collected. Specifically, the data are insufficient to establish attribution between a potential safety event and an individual using a ViiV Healthcare product as the study design is to analyse deidentified, secondary data collected from individual medical records. Therefore, a study specific pharmacovigilance plan will not be developed.

# 11. PLANS FOR DISSEMINATING AND COMMUNICATING STUDY RESULTS

#### 11.1. Milestones

This study-specific protocol will be submitted by 31 December 2020 for the EMA's review and endorsement. The study will start only after the protocol is approved by the EMA, and CAB LA and/or RPV LA is registered and commercially available in the relevant countries and is expected to continue through 2026 or later. Annual interim reports with cumulative data will be submitted and a final report is expected to be submitted in March 2027.

#### 11.2. Target Audience

The target audience for these data includes healthcare providers, regulatory and health authorities.

#### 11.3. Study reporting and publications

Interim and final study results will be included in safety and regulatory reports as appropriate. Study results will be made available externally through peer reviewed manuscript and conference presentation.

## **ANNEX 1. CASE REPORT FORM**

## C2C\_V1

C2C

Subject Label Expression: BSL:DEMOG:SUBJID

Date of Birth Expression:

Gender Expression:

Created: 09/08/2021 01:01

This page intentionally left blank

	Baseline	Antiretroviral Treatment	Resistance Testing	CAB + RPV LA Regimen	HIV RNA Viral Load/CD4 Count	Regimen Follow-up	Post-Switch Follow-Up	End of Study	Source Data Upload	Central Administration
Demographics and Consent	1									
Regimen Initiation	1									
Previous Virological Failure	R									
AIDS-Defining Events	1									
Concurrent Medications	1									
Comorbidities	1									
Antiretroviral Treatment		R	_							
Resistance Testing			R	_						
CAB+RPV LA regimen				R	_					
CD4 Count					R					
HIV RNA Viral Load					R					
6 Month Regimen Follow-up						1				
12 Month Regimen Follow-up						1				
24 Month Regimen Follow-up						1				
12 Months Post-Switch Follow-up							1			
24 Months Post-Switch Follow-up							1			
36 Months Post-Switch Follow-up							1			
48 Months Post-Switch Follow-up							1			
End of Study								1		
Sign Off								1		
Source Data Upload									1	
Central Administration										1

## **Demographics and Consent**

Subject ID SUBJID	
Inclusion Criteria	
Virologically suppressed (HIV-1 RNA <50 copies /mL) at the time of regimen initiation	○ No INC_VS ○ Yes
No evidence of prior virological failure with agents of the NNRTI and INI class	○ No INC_VF ○ Yes
No evidence of present or past recorded viral resistance to, and with agents of the NNRTI and INI class	○ No INC_VR ○ Yes
Consent	
Was patient consent required by local ethics approval?   No CONF	REQ
Was patient informed consent provided? No Yes	
Consent Date CONDAT	
Name of Consenting Clinician	
ICF Version Used	
Subjects at French Sites Only	
Confirm that the subject has been notified in writing of their participation in the study and personal data processing	○ Yes SUBINF
Demographics	
Age AGE	
Sex	
Route of HIV Infection	
Ethnicity	ETHNIC CONTROL OF CONT

**HIV Medical History** 

ID	CODE	NAME	EXP.CODE	TYPE	FMT/LEN	DERIVATION	CAT. VALUES
1	ZORNID	Subject ID	PORTID	Text	10	See Appendix	
2	INC_VS	suppressed (HIV-1 RNA <50 copies /mL	INC_VS	Category	3		N=No Y=Yes
3	INC_VF	No evidence of prior virological failure with agen	INC_VF	Category	3		N=No Y=Yes
4	INC_VR	No evidence of present or past recorded viral resi	INC_VR	Category	3		N=No Y=Yes
5	CONREQ	Was patient consert required by local ethics appro	CONREQ	Category	3		N=No Y=Yes
6	CON	Was patient informed consent provided?	CON	Category	3		N=No Y=Yes
7	CONDAT	Consent Date	CONDAT	Date/Time	dd/mm/yyyy		
8	CONNAM	Name of Consenting Clinician	CONNAM	Text	100		
9	ICFVER	ICF Version Used	ICFVER	Text	10		
10	SUBINF	Confirm that the subject has been notified in writ	SUBINF	Category	3		Y=Yes
11	AGE	Age	AGE	Integer	#99		
12	SEX	Sex	SEX	Category	6		M=Male F=Female
13	INFRT	Route of HIV Infection	I INFRT	Text	100		
14	ETHNIC	Ethnicity	ETHNIC	Category	26		See Appendix

eForm Code: DEMOG eForm Title: Demographics and Consent - Layout
Is HIV diagnosis date known?  No Yes
HIV diagnosis date  DIAGDAT
If date not known, please estimate number of years since diagnosis
Date of ART initiation ARTINDAT
HIV Subtype
HIV Subtype Group (if known)
Has the subject previously used an integrase inhibitor-based or NNRTI-based regimen  O  No  Yes
For Office Use Only
Data Daview Dassas Baview Data Natas for New Daview

Data Review Reason	Review Date	Э	Notes for Next Review
CRREAS	 CRDAT		CRNOT

#### eForm Code: DEMOG eForm Title: Demographics and Consent - Annotations Table

ID	CODE	NAME	EXP.CODE	TYPE	FMT/LEN	DERIVATION	CAT. VALUES
15	DIAGDTYN	Is HIV diagnosis date known?	DIAGDTYN	Category	3		N=No Y=Yes
16	DIAGDAT	HIV diagnosis date	DIAGDAT	Date/Time	dd/mm/yyyy		
17	DIAGYR	If date not known, please estimate number of years	DIAGYR	Integer	#9		
18	ARTINDAT	Date of ART Initiation	AKTINDAT	Date/Time	aa/mm/yyyy		
19	HIVSUB	HIV Subtype	HIVSUB	Category	5		1=HIV-1 2=HIV-2
20	HIVSUBGP	HIV Subtype Group (ii known)	HIVSUBGP	Text	50		
21	PREVNN	Has the subject previously used an integrase inhib	PREVNN	Category	3		N=No Y=Yes
Repeating Question Group: , Borders: Yes, RowStatus: Yes, RowNumbers: Yes, DisplayRows: 3, ÎnitialRows: 1, Min Repeats: 1, Max Repeats: 20, Main Row Type: Single-Line, Sub Row Type: Multi-Line							
22	CRREAS	Data Review Reason	CRREAS	Category	36, Optional		See Appendix
23	CRDAT	Review Date	CRDAT	Date/Time	dd/mm/yyyy, Optional		
24	CRNOT	Notes for Next Review	CRNOT	Text	500, Optional		

# Regimen Initiation

Regimen Initiation
Date CAB+RPV LA regimen started LASTDAT
Viral Load at Regimen Initiation  Please record sample taken on day of initiation, if possible.  Otherwise, please record last sample taken prior to regimen initiation
Date of sample VLDAT
Viral Load Greater Than or Less Than
HIV RNA viral load VLOAD
CD4 Count at Regimen Initiation  Please record sample taken on day of initiation, if possible.  Otherwise, please record last sample taken prior to regimen initiation
Date of Sample CD4DAT
CD4 Count CD4 Count Unit CD4UNIT
CD4 nadir prior to initiation of CAB+RPV LA CD4NAD CD4NAD CD4NAD CD4NAD
Height and Weight at Regimen Initiation
Are height and weight available at regimen initiation?  No Yes
Height (cm) HCM
Weight (kg) WKG
Is the BMI known? O No Yes
BMI BMI (Derived)

ID	CODE	NAME	EXP.CODE	TYPE	FMT/LEN	DERIVATION	CAT. VALUES
1	ZORNID_D	Subject ID	20R1ID D	Text	10	BSL:DEMOG:SUBJID	
2	LASTDAT	Date CAB+RPV LA regimen started	LASTDAT	Date/Time	dd/mm/yyyy		
3	VLDAT	Date of sample	VLDAT	Date/Time	dd/mm/yyyy		
4	VLGL	Viral Load Equal To, Greater Than or Less Than		Category	1, Optional		0=< 1=> 2==
5	VLOAD	HIV RNA viral load	VLOAD	Integer	#####9		
6	CD4DAT	Date of Sample	CD4DAT	Date/Time	aa/mm/yyyy		
7	CD4COUNT	CD4 Count	CD4COUNT	Real	######9.9###		
8	CD4UNIT	CD4 Count Unit	CD4UNIT	Category	9		1=cells/uL 2=10^9/L 3=10^6/L 4=Cells/mm3 5=10^3/uL
9	CD4NAD	CD4 nadir prior to initiation of CAB+RPV LA	CD4NAD	Real	######9.9### ###		
10	CD4NADU	CD4 Nadir Unit	CD4NADU	Category	9		1=cells/uL 2=10^9/L 3=10^6/L 4=Cells/mm3 5=10^3/uL
11	HWAVAIL	Are height and weight available at regimen initiat		Category	3		N=No Y=Yes
12	HCM		HCM	Integer	#99		
13	WKG	Weight (kg)	WKG	Integer	#99		
14	BMIYN		BMIYN	Category	3		N=No Y=Yes
15	BMI		BMI	Integer	99		
16	BMI_D	BMI (Derived)	BMI_D	Integer	99	WKG/(HCM*HCM)	

Data Review Reason	Review Date	Notes for Next Review
CRREAS	CRDAT	CRNOT

eForm Code: INIT eForm Title: Regimen Initiation - Layout

#### eForm Code: INIT eForm Title: Regimen Initiation - Annotations Table

ID	CODE	NAME	EXP.CODE	TYPE	FMT/LEN	DERIVATION	CAT. VALUES	
Repea	Repeating Question Group: , Borders: Yes, RowStatus: Yes, RowNumbers: Yes, DisplayRows: 3, InitiaRows: 1, Min Repeats: 1, Max Repeats: 20, Main Row Type: Single-Line, Sub Row Type: Multi-Line							
17	TCRREAS	Data Keview Keason	CRREAS	Category	36, Optional		See Appendix	
17	CKKLAS	Data Review Reason	CINIDAS	Category	30, Optional		эсе Аррениіх	
18		Review Date	CRDAT	Date/Time	dd/mm/yyyy, Optional			
19	CRNOT	Notes for Next Review	CRNOT	Text	500, Optional			

# Previous Virological Failure

Has subject experie virological failure?	enced previous	○ No ○ Yes
Date sample taken VFDAT	Viral Load Equal To, Greater Than or Less Th VFGL	HIV RNA viral load nan VFLOAD

Data Review Reason	Review Date	)	Notes for Next Review
CRREAS	CRDAT		CRNOT

ID	ZORJID_D CODE	NAME Subject ID	EXP.CODE	TYPE	FMT/LEN	DERIVATION  BSL:DEMOG:SUBJID	CAT. VALUES
2	VFYN	Has subject experienced previous virological failu		Category	3		N=No Y=Yes
Repeat	ing Question Group: , Boi	rders: Yes, RowStatus:	Yes, RowNumbers: Yo	es, DisplayRows: 3,	InitialRows: 1, Min	Repeats: 1, Max Repeats: 20, Main Row Type: Single-	Line, Sub Row Type: Multi-Line
	VFDAT	Date sample taken	IVEDAT	Date/Time	dd/mm/yyyy		
	VFGL	Viral Load Equal To, Greater Than or Less	VFGL	Category	1, Optional		0=< 1=> 2==
	VELOAD	I nan	1	Inhasan	######0		
Repeat	VFLOAD ing Ouestion Group: , Bo		VFLOAD Yes, RowNumbers: Ye	Integer es, DisplayRows: 3,	######9 InitialRows: 1, Min	   Repeats: 1, Max Repeats: 20, Main Row Type: Single-	Line, Sub Row Type; Multi-Line
		, , , , , , , , , , , , , , , , , , , ,		,,,,			
	CRREAS	Data Review Reason		Category	36, Optional		See Appendix
	CRDAT	Review Date	CRDAT	Date/Time	dd/mm/yyyy, Optional 500, Optional		
8	CRNOT	Notes for Next Review	CRNOT	Text	500, Optional		

eForm Code: AIDSDEF	eForm Title: AIDS-Defining Events - La	ayou

